- Non-investigational product(s), and/or medical device(s) or combination product(s) documentation, as applicable

Retention of study documents will be governed by the Clinical Trial Agreement.

Study and Site Closure

Amgen or its designee may stop the study or study site participation in the study for medical, safety, regulatory, administrative, or other reasons consistent with applicable laws, regulations, and GCP.

Both Amgen and the Investigator reserve the right to terminate the Investigator's participation in the study according to the Clinical Trial Agreement. The investigator is to notify the IRB/IEC in writing of the study's completion or early termination and send a copy of the notification to Amgen.

Subjects may be eligible for continued treatment with Amgen investigational product(s) by an extension protocol or as provided for by the local country's regulatory mechanism. However, Amgen reserves the unilateral right, at its sole discretion, to determine whether to supply Amgen investigational product(s) and by what mechanism, after termination of the study and before the product(s) is/are available commercially.

Compensation

Any arrangements for compensation to subjects for injury or illness that arises in the study are described in the Compensation for Injury section of the Informed Consent that is available as a separate document.

Appendix 4. Safety Events: Definitions and Procedures for Recording, Evaluating, Follow-up and Reporting

Definition of Disease-related Event

Disease-related Event Definition

• Disease-related events are events (serious or non-serious) anticipated to occur in the study population due to the underlying disease. See Appendix 11 for a list of disease-related events. All serious disease-related events will be recorded and reported to the sponsor or designee within 24 hours.• Disease-related events that would qualify as an adverse event or serious adverse event:
○ An event based on the underlying disease that is worse than expected as assessed by the investigator for the subject's condition or if the investigator believes there is a causal relationship between the investigational product(s)/study treatment/protocol-required therapies and disease worsening, this must be reported as an adverse event or serious adverse event.• Disease-related events that do not qualify as adverse events or serious adverse events:
○ An event which is part of the normal course of disease under study (eg, disease progression in oncology or hospitalization due to disease progression) is to be reported as a disease-related event.

Definition of Adverse Event

Adverse Event Definition

• An adverse event is any untoward medical occurrence in a clinical study subject irrespective of a causal relationship with the study treatment.• Note: An adverse event can therefore be any unfavorable and unintended sign (including an abnormal laboratory finding), symptom, or disease (new or exacerbated) temporally associated with the use of a treatment, combination product, medical device or procedure.• Note: Treatment-emergent adverse events will be defined in the statistical analysis plan (SAP).

Events Meeting the Adverse Event Definition

- Any abnormal laboratory test results (hematology, clinical chemistry, or urinalysis) or other safety assessments (eg, electrocardiogram [ECG], radiological scans, vital signs measurements), including those that worsen from baseline, that are considered clinically significant in the medical and scientific judgment of the investigator (ie, not related to progression of underlying disease).
- Exacerbation of a chronic or intermittent pre-existing condition including either an increase in frequency and/or intensity of the condition.
- New conditions detected or diagnosed after study treatment administration even though it may have been present before the start of the study.
- Signs, symptoms, or the clinical sequelae of a suspected drug-drug interaction.
- Signs, symptoms, or the clinical sequelae of a suspected overdose of either study treatment or a concomitant medication. Overdose per se will not be reported as an adverse event/serious adverse event unless it is an intentional overdose taken with possible suicidal/self-harming intent. Such overdoses are to be reported regardless of sequelae.
- The signs, symptoms, and/or clinical sequelae resulting from lack of efficacy will be reported as adverse event or serious adverse event if they fulfill the definition of an adverse event or serious adverse event. Also, “lack of efficacy” or “failure of expected pharmacological action” also constitutes an adverse event or serious adverse event.

Events NOT Meeting the Adverse Event Definition

- Medical or surgical procedure (eg, endoscopy, appendectomy): the condition that leads to the procedure is the adverse event.
- Situations in which an untoward medical occurrence did not occur (social and/or convenience admission to a hospital).
- Anticipated day-to-day fluctuations of pre-existing disease(s) or condition(s) present or detected at the start of the study that do not worsen.

Definition of Serious Adverse Event

A Serious Adverse Event is defined as any untoward medical occurrence that, meets at least 1 of the following serious criteria:	

• Results in death (fatal)	

• Immediately life-threatening The term "life-threatening" in the definition of "serious" refers to an event in which the subject was at risk of death at the time of the event. It does not refer to an event, which hypothetically might have caused death, if it were more severe.	

• Requires in-patient hospitalization or prolongation of existing hospitalization In general, hospitalization signifies that the subject has been detained (usually involving at least an overnight stay) at the hospital or emergency ward for observation and/or treatment that would not have been appropriate in the physician's office or outpatient setting. Complications that occur during hospitalization are an adverse event. If a complication prolongs hospitalization or fulfills any other serious criteria, the event is serious. When in doubt as to whether "hospitalization" occurred or was necessary, the adverse event is to be considered serious. Hospitalization for elective treatment of a pre-existing condition that did not worsen from baseline is not considered an adverse event.	

• Results in persistent or significant disability/incapacity The term disability means a substantial disruption of a person's ability to conduct normal life functions. This definition is not intended to include experiences of relatively minor medical significance such as uncomplicated headache, nausea, vomiting, diarrhea, influenza, and accidental trauma (eg, sprained ankle) which may interfere with or prevent everyday life functions but do not constitute a substantial disruption.	

• Is a congenital anomaly/birth defect	

• Other medically important serious event Medical or scientific judgment is to be exercised in deciding whether serious adverse event reporting is appropriate in other situations such as important medical events that may not be immediately life-threatening or result in death or hospitalization but may jeopardize the subject or may require medical or surgical intervention to prevent 1 of the other outcomes listed in the above definition. These events are typically to be considered serious. Examples of such events include invasive or malignant cancers, intensive treatment in an emergency room or at home for allergic bronchospasm, blood dyscrasias or convulsions that do not result in hospitalization, or development of drug dependency or drug abuse.	

Recording Adverse Events, Disease-related Events (if applicable), and Serious Adverse Events

Adverse Event, Disease-related Event (if applicable) and Serious Adverse Event Recording

• When an adverse event, disease-related event or serious adverse event occurs, it is the responsibility of the investigator to review all documentation (eg, hospital progress notes, laboratory, and diagnostics reports) related to the event.• The investigator will then record all relevant adverse event/disease-related event/serious adverse event information in the Event case report form (CRF).

- Additionally, the investigator is required to report a fatal disease-related event on the Event CRF.
- The investigator must assign the following adverse event attributes:
 - Adverse event diagnosis or syndrome(s), if known (if not known, signs or symptoms);
 - Dates of onset and resolution (if resolved);
 - Did the event start prior to first dose of investigational product;
 - Assessment of seriousness;
 - Severity (or toxicity defined below);
 - Assessment of relatedness to efavaleukin alfa;
 - Action taken; and
 - Outcome of event.
- If the severity of an adverse event changes from the date of onset to the date of resolution, record as a single event with the worst severity on the Event CRF.
- It is not acceptable for the investigator to send photocopies of the subject's medical records to the sponsor in lieu of completion of the Event CRF page.
- If specifically requested, the investigator may need to provide additional follow-up information, such as discharge summaries, medical records, or extracts from the medical records. In this case, all subject identifiers, with the exception of the subject number, will be blinded on the copies of the medical records before submission to the sponsor.
- The investigator will attempt to establish a diagnosis of the event based on signs, symptoms, and/or other clinical information. In such cases, the diagnosis (not the individual signs/symptoms) will be documented as the adverse event/serious adverse event.

Evaluating Adverse Events and Serious Adverse Events

Assessment of Severity

The investigator will make an assessment of severity for each adverse event and serious adverse event reported during the study. The assessment of severity will be based on:
 
The Common Terminology Criteria for Adverse Events (CTCAE), version 4.03 which is available at the following location:
 
http://ctep.cancer.gov/protocolDevelopment/electronic_applications/ctc.htm.

Assessment of Causality

• The investigator is obligated to assess the relationship between investigational product and/or study-mandated procedure and each occurrence of each adverse event/serious adverse event.• Relatedness means that there are facts or reasons to support a relationship between investigational product and the event.• The investigator will use clinical judgment to determine the relationship.• Alternative causes, such as underlying disease(s), concomitant therapy, and other risk factors, as well as the temporal relationship of the event to study treatment administration will be considered and investigated.• The investigator will also consult the Investigator's Brochure and/or Product Information, for marketed products, in his/her assessment.• For each adverse event/serious adverse event, the investigator must document in the medical notes that he/she has reviewed the adverse event/serious adverse event and has provided an assessment of causality.• There may be situations in which a serious adverse event has occurred and the investigator has minimal information to include in the initial report. However, it is very important that the investigator always make an assessment of causality for every event before the initial transmission of the serious adverse event data.• The investigator may change his/her opinion of causality in light of follow-up information and send a serious adverse event follow-up report with the updated causality assessment.• The causality assessment is 1 of the criteria used when determining regulatory reporting requirements.

Follow-up of Adverse Event and Serious Adverse Event

- The investigator is obligated to perform or arrange for the conduct of supplemental measurements and/or evaluations as medically indicated or as requested by Amgen to elucidate the nature and/or causality of the adverse event or serious adverse event as fully as possible. This may include additional laboratory tests or investigations, histopathological examinations, or consultation with other health care professionals.
- If a subject is permanently withdrawn from protocol-required therapies because of a serious adverse event, this information must be submitted to Amgen.
- If a subject dies during participation in the study or during a recognized follow-up period, the investigator will provide Amgen with a copy of any post-mortem findings including histopathology.
- New or updated information will be recorded in the originally completed Event CRF.
- The investigator will submit any updated serious adverse event data to Amgen within 24 hours of receipt of the information.

Reporting of Serious Adverse Event

Serious Adverse Event Reporting via Electronic Data Collection Tool

- The primary mechanism for reporting serious adverse event will be the electronic data capture (EDC) system.
- If the EDC system is unavailable for more than 24 hours, then the site will report the information to Amgen using a paper-based electronic Serious Adverse Event (eSAE) Contingency Report Form (see [Figure 12-1](#)) within 24 hours of the investigator's knowledge of the event.
- The site will enter the serious adverse event data into the electronic system as soon as it becomes available.
- After the study is completed at a given site, the EDC system will be taken off-line to prevent the entry of new data or changes to existing data.
- If a site receives a report of a new serious adverse event from a study subject or receives updated data on a previously reported serious adverse event after the EDC system has been taken off-line, then the site can report this information on the paper-based Serious Adverse Event Contingency Report Form (see [Figure 12-1](#)).
- Once the study has ended, serious adverse event(s) should be reported to Amgen (regardless of causality) if the investigator becomes aware of a serious adverse event. The investigator should use the paper-based Serious Adverse Event Contingency Report Form to report the event.

Figure 12-1. Sample Electronic Serious Adverse Event Contingency Form

AMGEN Study # 20160283 AMG 592		Electronic Serious Adverse Event Contingency Report Form For Restricted Use						
Reason for reporting this event via fax								
The Clinical Trial Database (eg. Rave):								
 Is not available due to internet outage at my site  Is not yet available for this study  Has been closed for this study								
<<For completion by COM prior to providing to sites: SELECT OR TYPE IN A FAX#>>								

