Appendix 3. Study Governance Considerations

Dose Level Review Meetings

After all dose limiting toxicity (DLT)-evaluable subjects within a cohort have completed the 4-week DLT evaluation period, a dose level review meeting (DLRM) will be conducted to review and interpret safety data for the purposes of making recommendations about dose-level changes and evaluating safety signals. In addition, ad hoc DLRMs may be convened by the Medical Monitor at any time for review of emerging safety events.

The required Dose Level Review Team (DLRT) members are the Medical Monitor, Global Safety Officer (GSO), and Site Investigators. Optional non-voting Amgen representatives may also attend as needed at the discretion of the Medical Monitor, including but not limited to representatives from Study management, Biostatistics, Clinical Pharmacology, and Clinical Biomarkers.

For a DLRM to occur, the Medical Monitor must be in attendance and cannot be represented by a voting designee or delegate. Voting designees can be identified as appropriate by the GSO or Site Investigator(s). In addition, a quorum of Site Investigators must attend. A quorum is defined as greater than 50% of the participating investigators or their qualified designee. The DLRM will be rescheduled if these requirements are not met. A Site Investigator may identify a delegate (eg, Sub-investigator) who is listed in the Delegation of Authority. If a delegate attends in place of a Site Investigator, the Site Investigator must provide written agreement with the delegate's vote.

The DLRT members will be responsible for dosing recommendations, which may include escalation to the next planned dose, adding additional cohorts, escalation to an intermediate dose (a dose lower than the next planned dose), de-escalation to a lower dose; continuation, delay, or termination of dosing; or removal, repetition or expansion of a cohort.

All available study data including demographics, investigational product administration, medical history, concomitant medications, adverse events, electrocardiograms (ECGs), vital signs, and laboratory results. All available safety data, including data collected after the DLT evaluation period will be included. Data to be reviewed may be unqueried.

DLRM voting will occur as follows. There will be a total of 3 votes: 1 for the Medical Monitor, 1 for the GSO or delegate, and 1 for all of the Site Investigators or delegates

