combined. Regardless of how many Site Investigators there are, all of the Site Investigators combined will have a total of one vote decided by a majority of the investigators (defined as greater than or equal to 50%).

DLRT recommendations to escalate to the next planned cohort, or to an intermediate cohort, must be by unanimous vote. If the DLRT is not able to reach a unanimous recommendation on whether to escalate to the next planned cohort or to an intermediate cohort, then this should be reflected in the DLRM Memo. Other recommendations, such as expanding a cohort or lowering a dose can be made by a majority vote.

The dosing change recommendations will be documented in the DLRM Memo. After receiving the DLRT recommendation, Amgen will render a final decision and will issue a written notification of the dose change decision to study investigators. Amgen retains final decision-making authority on all dose escalation/changes.

Dose Level Determination

The Medical Monitor will determine if a DLRM is necessary based on the cohort status and all available safety data. Recommendations to escalate to a higher dose cohort will only occur when the previous dose regimen(s) has (have) been found to be reasonably tolerated based on available study data through the last subject in a dosing cohort's 4-week DLT evaluation period and upon unanimous agreement of the 3 DLRM votes. Dosing recommendations will be made on a treatment cohort basis (not on an individual basis).

Regulatory and Ethical Considerations

This study will be conducted in accordance with the protocol and with:

- Consensus ethical principles derived from international guidelines including the Declaration of Helsinki and Council for International Organizations of Medical Sciences (CIOMS) International Ethical Guidelines
- Applicable ICH Good Clinical Practice (GCP) Guidelines
- Applicable laws and regulations

The protocol, protocol amendments, informed consent form, Investigator's Brochure, and other relevant documents (eg, subject recruitment advertisements) must be submitted to an IRB/IEC by the investigator and reviewed and approved by the IRB/IEC. A copy of the written approval of the protocol and informed consent form must be received by Amgen before recruitment of subjects into the study and shipment of Amgen investigational product.

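### The dose level review meeting counts 50% of investigators as a majority, so a tied investigator vote has no defined safe outcome and escalation can be recorded as unanimous with half of them opposed

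*Protocol*

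**What the plan says.** The rule is in Protocol Appendix 3, under Dose Level Review Meetings and Dose Level Determination.

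- Votes: "There will be a total of 3 votes: 1 for the Medical Monitor, 1 for the GSO or delegate, and 1 for all"; this last vote is shared by every Site Investigator or delegate. However many investigators there are, "all of the Site Investigators combined will have a total of one vote".
- How that shared vote is settled: it is "decided by a majority of the investigators (defined as greater than or equal to 50" per cent).
- Escalation: "DLRT recommendations to escalate to the next planned cohort, or to an intermediate cohort, must be by unanimous vote". Dose Level Determination repeats the condition as "upon unanimous agreement of the 3 DLRM votes", so unanimity is counted over the three votes and not over individual investigators.
- Quorum: "A quorum is defined as greater than 50% of the participating investigators or their qualified designee". Here the inequality is strict.
- Failure to agree on escalation is to be noted in the DLRM Memo. Other recommendations, such as expanding a cohort or lowering a dose, need only a majority of the three votes.
- The review team recommends; the sponsor takes the final decision.

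SAP Section 7.1, which covers the DLRMs, contains no voting rule. Neither document says how an evenly split investigator vote is recorded.

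**The concern.** A majority is normally more than half. Setting the threshold at half or more means that two opposite positions can both reach it. That matters because of where the vote sits. Protocol Section 5.1.1 describes the Medical Monitor and the GSO as the sponsor's, so the investigators hold the only non-sponsor vote of the three. Requiring all three votes is meant to give them a veto over an escalation recommendation. At an exact tie the text does not say whether that veto has been exercised.

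At stake is whether a memo recording unanimity can be relied on to mean that the investigators supported going to a higher dose.

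**Working it through.** The plan states no figure on this point, so there is nothing to reproduce. The check is an enumeration of the voting rule, followed by a rough sizing.

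**Inputs.** Threshold of at least 50%, three votes, unanimity for escalation, and quorum above 50%, all from Protocol Appendix 3. About 14 phase 1b sites, from Protocol Section 5.2.2. Assumptions of this check: one voting investigator per site, and the percentage taken among those voting.

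**Step 1: when do both sides reach the threshold?** Let n investigators vote and k vote yes. Both sides qualify when k/n ≥ 0.5 and (n − k)/n ≥ 0.5, which together give k = n/2. This is possible at every even n and never at odd n.

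**Step 2: smallest yes count, and the share that can be opposed.**

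| n voting | Yes votes needed at ≥ 50% | Opposed | Yes votes needed at > 50% | Opposed |
|---|---|---|---|---|
| 2 | 1 | 50% | 2 | 0% |
| 4 | 2 | 50% | 3 | 25% |
| 6 | 3 | 50% | 4 | 33.3% |
| 8 | 4 | 50% | 5 | 37.5% |
| 10 | 5 | 50% | 6 | 40% |
| 12 | 6 | 50% | 7 | 41.7% |
| 14 | 7 | 50% | 8 | 42.9% |

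At odd n the two thresholds coincide (for example 4 of 7, or 7 of 13).

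**Step 3: an example at the planned size.** With 14 investigators the quorum is 14/2 + 1 = 8. If 8 attend and split 4 to 4, each side has 4/8 = 50%. Record that as yes, add yes from the Medical Monitor and the GSO, and the result is 3 of 3 votes with 4 of 8 investigators opposed. Record it as no, and the recommendation fails. The text permits either entry.

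**Step 4: the denominator.** Appendix 3 does not say whether the 50% is of those attending or of all participating investigators. If it is of all 14, the 4 to 4 split gives each side 4/14 = 28.6% and neither side reaches the threshold. Both sides would then reach it only if all 14 voted and split 7 to 7.

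**Step 5: how often.** If each investigator votes yes independently with probability p, the tie probability is C(n, n/2) × [p(1 − p)]^(n/2). Because p(1 − p) is largest at p = 0.5, that value is the upper bound within this model.

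- n = 8, p = 0.5: 70/256 = 27.3%.
- n = 8, p = 0.8: 70 × 0.16^4 = 4.6%.
- n = 14, p = 0.5: 3432/16384 = 20.9%.
- n = 14, p = 0.8: 3432 × 0.16^7 = 0.9%.
- Any odd n: 0%.

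The documents give no value for p. A tie also changes an escalation recommendation only when both sponsor votes are yes, which these figures leave out.

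**The case against.** The strongest reply is that the definition is a pass threshold on the motion: the investigators' vote is yes if at least half support it. A tie then has a definite result and nothing is contradictory. That reading is open, but it does not help, because it settles every tie in favour of escalation.

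A second reply is that the sponsor decides anyway. This is true and limits the consequence. It does not repair the rule, because Appendix 3 makes unanimity a condition for the escalation recommendation itself, and a tie leaves it unclear whether that condition is met. The provision for noting non-unanimity in the memo has the same difficulty: it applies only once someone has decided that the tie was not a yes.

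A third reply is that nothing is left to protect. SAP Sections 1 and 3.1 report early termination, cancellation of the expansion cohort and of phase 2, and an end to enrolment in cohort 5 at its planned dose. This stands, and it keeps the point minor.

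A reader might also infer three stronger things that the documents do not support:

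- That the investigators' vote is the only independent safeguard. It is the only non-sponsor vote, but Appendix 3 separately requires that the previous regimen was reasonably tolerated through the last subject's 4-week evaluation period, and it allows ad hoc meetings. After a first dose-limiting toxicity, model results also go to the meeting (Protocol Section 5.1.1), although SAP Section 9.6.2.1 calls them non-binding.
- That ties would occur in a fifth to a quarter of meetings. Those figures assume independent votes at even odds, and investigators looking at the same data are unlikely to vote that way.
- That some escalation in this trial rested on a tie. Neither document reports a vote count.

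**Conclusion.** The point holds as a flaw in a stated decision threshold, with small practical weight. At any even number voting, an exact tie either satisfies the definition for both sides or counts as yes, and no tie-break exists. An escalation recommendation can therefore be recorded as unanimous with 50% of the voting investigators opposed, provided the Medical Monitor and the GSO both vote yes.

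This conclusion rests on an even number voting and on the percentage being taken among those voting. With all participating investigators as denominator, it narrows to a full turnout split exactly in half. The tie probabilities in the working illustrate size and do not forecast frequency. The rule is ambiguous rather than always permissive, since a tie can equally be entered as a no.

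**What to change.** In Appendix 3, define the investigators' combined vote as more than 50% of those voting, and state that a tie is not a vote in favour of escalation. This settles the threshold, the denominator and the tie together. The same sentence should say how a tie is recorded for the other recommendations, where the investigators' vote can decide the result if the two sponsor votes differ. It is a change to meeting procedure and touches no dose or clinical rule.

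The cost is one phrase. Nothing changes at odd numbers. At even numbers one more yes vote is needed, so a tied panel blocks a unanimous escalation recommendation, and the outcome goes into the DLRM Memo as Appendix 3 already provides.

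If no further amendment is planned, the sponsor can check the existing memos for any escalation recommendation that relied on a tied investigator vote, and correct the wording wherever this appendix text is reused.
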